6.2.1. Analysis of Secondary Efficacy Endpoints

The FAPS will be the primary analysis set for key secondary efficacy endpoints and time to COVID-19 symptom alleviation. The Virology Analysis Set will be the primary analysis set for SARS-CoV-2 nasal swab viral load.

The key secondary endpoints will be tested in the following sequential order using a gatekeeping approach:

- 1. Proportion of participants with all-cause hospitalization by Day 29
- 2. Proportion of participants with COVID-19-related MAVs or all-cause death by Day 29
- 3. Proportion of participants with COVID-19-related MAVs by Day 29
- 4. Proportion of participants with all-cause death by Day 29

The proportion of participants with all-cause hospitalization by Day 29, COVID-19–related MAVs or all-cause death by Day 29, COVID-19 related MAVs by Day 29, and all-cause death by Day 29 will be analyzed in a similar manner to the primary endpoint.

All-cause death by Day 29 will also be compared between the 2 treatment groups using the Fisher's exact test. If a participant prematurely discontinues from the study prior to Day 29 and the death status is missing, the participant will not be included in the analysis.

The Kaplan-Meier product limit method will be used to estimate, and stratified log-rank test will be used to compare the 2 treatment groups for the time to COVID-19 symptom alleviation by Day 15. In addition, a Cox proportional hazards regression model with the stratification factors as covariates will be used to estimate the hazard ratio and its 2-sided 95% CI.

Change from baseline in SARS-CoV-2 nasal swab viral load to each visit including Day 5 will be compared between the 2 treatment groups using a mixed-effects model repeated measures (MMRM) approach. Additionally, change in SARS-CoV-2 viral load from baseline at each postbaseline analysis visit will be provided. Descriptive statistics will be provided by treatment group as follows: (1) Baseline values, (2) Values at each postbaseline analysis visit, (3) Change from baseline at each postbaseline analysis visit. **CCI**

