3.3. Strata and Covariates

Participants will be randomly assigned to treatment groups via the interactive voice or web response system (IXRS) in a 1:1 ratio using a stratified randomization schedule. Stratification will be based on the following variables:

- Duration of symptoms at enrollment: ≤ 3 days versus > 3 days
- Vaccination status: ever versus never

If there are discrepancies in stratification factor values between the IXRS and the clinical database, the values recorded in the clinical database will be used for analyses. Additionally, stratification discrepancies will be reviewed and assessed. Based on the assessment of stratification discrepancies, a sensitivity analysis of the primary endpoint may be performed.

The primary efficacy endpoint will be evaluated using stratification factors as covariates or stratification variables for analyses, as specified in Section 6. If there is an imbalance in presumed prognostic baseline characteristics between treatment groups, efficacy evaluations may

be performed that include these baseline values in efficacy analysis models as covariates; these evaluations will be considered sensitivity analyses.

If 5 events or fewer across both treatment groups are observed within 1 or more stratum, the primary and key secondary endpoints will be evaluated in the same analyses without using the corresponding stratification factor(s).

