5.2. Other Baseline Characteristics

The following baseline disease characteristics will be summarized by treatment group and overall using descriptive statistics for continuous variables and using number and percentage of participants for categorical variables for the Safety Analysis Set and FAPS:

- Randomization strata: duration of symptoms at enrollment (≤ 3 days versus > 3 days); vaccination status (ever versus never)
- Duration of COVID-19 symptoms prior to first dose of study drug
- Duration from first positive SARS-CoV-2 diagnostic test to first dose of study drug
- Risk factors defined in the inclusion criteria
- Total number of risk factors
- Number of targeted COVID-19 symptoms at baseline measured via the SIC questionnaire
- Summary for each COVID-19 targeted symptom at baseline, where an answer "No" to the questions will be considered as 0 in the summary of severity rating

- Baseline seropositivity: overall positive, ie, anti-spike antibody positive or anti-nucleocapsid antibody positive, versus overall negative, ie, both anti-spike antibody and anti-nucleocapsid antibody negative
- Baseline respiratory viral coinfections: None; Yes subdivided into: Influenza A; Influenza B; respiratory syncytial virus (RSV)
- Baseline SARS-CoV-2 viral load (as a continuous variable, and a categorical variable with $< 6 \log_{10} \text{ copies/mL versus} \ge 6 \log_{10} \text{ copies/mL})$
- Baseline eGFR: Creatinine Clearance by Cockcroft-Gault: \ge 90 mL/min, \ge 60–< 90 mL/min, \ge 30 < 60 mL/min, < 30 mL/min

For categorical data, the CMH test (ie, general association statistic for nominal data and row mean scores for ordinal data) will be used to compare the 2 treatment groups. For continuous data, the 2-sided Wilcoxon rank sum test will be used to compare the 2 treatment groups.

Similar summaries (except randomization strata) will be provided for the following subgroups corresponding to randomization strata: duration of symptoms at enrollment (\leq 3 days versus > 3 days); vaccination status (ever versus never).

A by-participant listing of other baseline characteristics will be provided by participant ID number in ascending order.

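### Time to symptom alleviation is adjusted only for the two randomization factors; prespecifying the baseline symptom count, already derived, could recover some efficiency, of unknown size

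*SAP*

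**What the plan says.** SAP 6.2.1 says that Kaplan-Meier curves will be estimated and that a "stratified log-rank test will be used to compare the 2 treatment groups for the time to COVID-19 symptom alleviation by Day 15". The treatment effect is estimated separately, since the same section states that "a Cox proportional hazards regression model with the stratification factors as covariates will be used to estimate the hazard ratio and its 2-sided 95% CI". SAP 3.3 lists the stratification factors: "Duration of symptoms at enrollment: ≤ 3 days versus > 3 days" and "Vaccination status: ever versus never". Neither measures how many symptoms a participant has or how severe they are.

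SAP 5.2 includes both kinds of information among the baseline summaries: "Number of targeted COVID-19 symptoms at baseline measured via the SIC questionnaire" and "Summary for each COVID-19 targeted symptom at baseline", with an answer of No scored as 0. Neither enters a model in 6.2.1.

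Other baseline covariates are covered only by a general provision in SAP 3.3, which applies when the arms turn out to differ on variables thought to be prognostic. In that case extra analyses can "be performed that include these baseline values in efficacy analysis models as covariates; these evaluations will be considered sensitivity analyses".

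SAP 6.2 places this endpoint among the other secondary endpoints, after the four alpha-controlled ones. Protocol 8.5.2 names only Kaplan-Meier and a log-rank test for it.

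**The concern.** Under SAP 6.2 and Appendix 3, alleviation needs all 15 targeted symptoms to be rated 0, answered No, or at least 3 points below baseline, held for 48 consecutive hours. The slowest symptom therefore sets the time. Other things equal, a participant who starts with more symptoms should take longer. Protocol 4.2 requires only one symptom at randomization, so starting burden can vary widely.

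Leaving a prognostic baseline variable out of a proportional hazards analysis moves the estimated treatment hazard ratio toward 1 and reduces the power of the test. Covariates chosen because an imbalance was seen (SAP 3.3) do not replace prespecified adjustment. The efficiency gain comes from explaining outcome variation, whether or not the arms happen to be imbalanced.

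The matter carries some weight here because SAP 2.3 reports that enrollment stopped below half of plan after a lower-than-expected primary event rate. Alleviation is likely to occur in many more participants than the primary endpoint does, although the documents give no alleviation rate.

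**Working it through.** **Plan's own figure.** No power, effect size or alleviation rate is stated for this endpoint. The power in SAP 1.3 is for the primary endpoint. It reproduces: expected events are 1150 × 0.02 + 1150 × 0.005 = 28.75, and power is 90.0% (two proportions), 89.6% (Freedman) or 96.1% (Schoenfeld), against the stated figure of about 90%. It has no bearing on symptom alleviation.

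**Inputs from the documents.** 1:1 allocation (SAP 1.2), censoring at Day 14 (SAP Appendix 3), and fewer than 0.5 × 2300 = 1150 randomized (SAP 2.3).

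**Inputs assumed.** Conditional treatment hazard ratio 1.2; N = 800 or 1140; 60% or 80% of placebo participants alleviated by Day 14; two-sided 0.05; one standard normal baseline score x with a log-linear effect.

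**Method.** The hazard for a participant is λ·exp(log(1.2)·treatment + g·x), with λ set to give the assumed placebo alleviation rate. Times are exponential. Each setting has 1000 simulated trials. Each trial is analyzed by Cox with treatment alone, which stands in for the log-rank test, and by Cox with treatment and x. The two randomization factors are not simulated.

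Power in percent, unadjusted → adjusted (hazard ratio per SD is for slower alleviation with greater burden):

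| HR per SD | N 800, 60% | N 800, 80% | N 1140, 60% | N 1140, 80% | Gain, points |
|---|---|---|---|---|---|
| 1.00 | 54.9 → 54.8 | 66.7 → 66.6 | 71.1 → 70.6 | 78.1 → 77.9 | none |
| 0.78 | 53.4 → 54.6 | 61.9 → 64.6 | 64.1 → 67.7 | 74.3 → 78.1 | 1-4 |
| 0.61 | 46.3 → 52.9 | 53.9 → 64.2 | 59.5 → 69.3 | 65.8 → 77.3 | 7-12 |
| 0.47 | 38.6 → 55.5 | 42.7 → 63.1 | 52.6 → 68.1 | 59.0 → 79.8 | 16-21 |
| 0.37 | 29.7 → 49.3 | 35.4 → 61.7 | 43.1 → 68.6 | 44.5 → 74.6 | 20-30 |

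The Monte Carlo standard error of each power is at most √(0.25/1000) = 1.6 points. Both analyses use the same simulated trials, which steadies the differences, but the smallest gains are still close to noise. The mean unadjusted hazard ratio runs from about 1.20 with no prognostic effect down to 1.13 at the strongest; the adjusted one stays near 1.20.

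**How prognostic might the count be?** A separate simulation of the all-symptoms-must-clear rule used N = 1000, lognormal clearance times, within-person correlation 0.3 to 0.9, and no 3-point rule. It gave a log hazard ratio for the count of about -0.27 to -0.08 per SD. That is a hazard ratio of exp(-0.27) = 0.76 to exp(-0.08) = 0.92, and effective sample size rose by only 1-3%. These values depend on the assumed clearance times and spread of counts. They support the mechanism, but they place the count alone at the low end of the table.

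**The case against.** The strongest objection is that this is an ordinary, valid choice and the gain is assumed rather than shown. A reader might infer that baseline burden largely determines time to alleviation, so that substantial power is being given away on a main secondary endpoint. The documents do not support that reading, for four reasons.

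- They contain no data on how strongly baseline symptoms predict the outcome. The two lower rows of the table follow from the assumed strength alone.
- The endpoint is partly relative to baseline. A rating of 10 need only fall to 7, while a rating of 1, 2 or 3 must reach 0 or No. If ratings decayed proportionally at rate k, a 10 would qualify after ln(10/7)/k = 0.36/k, but a 3 would round to 0 only after ln(3/0.5)/k = 1.79/k. Greater severity could therefore mean earlier alleviation, while a higher count acts the other way.
- The endpoint is not a main one. It has no alpha allocation and no planned power.
- The Cox model quoted from 6.2.1 supplies the estimate, not the test. Adding a covariate there alone would leave the log-rank test and its power unchanged.

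All four stand. So does the point that the shift from 1.20 toward 1.13 reflects a marginal rather than a conditional hazard ratio, not bias in the planned test. If burden is correlated with symptom duration, part of any gain is already captured by that stratum.

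Two further defenses do not remove the point. The SAP 3.3 provision depends on seeing an imbalance and yields only sensitivity analyses. The redacted text following 6.2.1 may contain other symptom analyses, but nothing readable shows an adjusted one.

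**Conclusion.** The point holds as an optional efficiency improvement, not as an error in the plan. A baseline variable that is already derived, and that has a plausible structural link to the outcome, is left out of both the test and the model. In the simulation, adjustment cost essentially no power when the variable had no prognostic effect.

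The size is unknown: nil if burden is not prognostic, 1-4 power points at a hazard ratio of 0.78 per SD, and 7-12 points at 0.61 per SD. These rest on an assumed treatment hazard ratio of 1.2, 60-80% of placebo participants alleviated, 800 to 1140 participants and a log-linear baseline effect. For the count alone, the lower part of that range is the more credible. Type I error and the alpha-controlled endpoints are unaffected.

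**What to change.** In SAP 6.2.1, before unblinding:

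1. Add the baseline number of targeted symptoms (SAP 5.2) as a covariate in the Cox model for time to alleviation, with a missing-baseline indicator so that nobody is dropped. Participants without baseline data already face a stricter alleviation rule (SAP 6.2), which is a further reason to identify them separately.
2. Take the treatment test from that adjusted model, or stratify the log-rank test by category of baseline count. Three categories crossed with the four randomization cells would give 12 strata before any missing category, so the model-based test is simpler.
3. State that the hazard ratio is conditional on baseline burden, and show the currently planned stratified log-rank test and Cox estimate beside it.
4. Record the change of test in SAP 6.5. If treatment codes are already open, label the adjusted analysis supportive.

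The count is preferable to a total severity score. In the SIC form reproduced in SAP Appendix 2, fever is recorded as a temperature and shaking or shivering shows no 0-10 rating, so a 15-item total would need new scoring rules. Every item has a Yes/No answer.

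The cost is a few lines of text, two model terms and one extra row of results, with no new data. The drawback is a second hazard ratio with a different interpretation, which the report must explain.

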6.4. Intercurrent Events

Handling of intercurrent events for the efficacy endpoints related to hospitalization, MAVs, death, symptom alleviation, SARS-CoV-2 viral load, or SARS-CoV-2 infectious viral titer are shown in Table 6-1. Intercurrent events are events occurring after treatment initiation that affect either the interpretation or the existence of the measurement of an endpoint. An event (eg, use of rescue medication) that occurs after an endpoint of interest (eg, hospitalization) is not considered as an intercurrent event.

Endpoint	Intercurrent event	Strategy	Description		
Proportion of COVID-19–related hospitalization or all-cause death by Day 29 Proportion of participants with all-cause hospitalization by Day 29	Discontinue randomized treatment prior to endpoint (due to AE, lack of efficacy, investigator's discretion, noncompliance with study drug, protocol violation, participant decision, lost to follow-up)	Treatment policy	Ignore the occurrence of intercurrent events (use observed outcome)		
Proportion of participants with COVID-19–related MAVs or all-cause death by Day 29 Proportion of participants with COVID-19–related MAVs by Day 29	Use of rescue medication	Treatment policy	Ignore the occurrence of intercurrent events (use observed outcome)		
Proportion of participants with all-cause death by Day 29					

Table 6-1.Handling of Intercurrent Events

Endpoint	Intercurrent event	Strategy	Description		
	Hospitalization for the treatment of COVID-19 or all-cause death	Composite policy	Hospitalization for the treatment of COVID-19 or all-cause death means never achieve symptom alleviation (censored at Day 14)		
Time to COVID-19 symptom alleviation by Day 15	Discontinue randomized treatment prior to symptom alleviation (due to AE, lack of efficacy, investigator's discretion, noncompliance with study drug, protocol violation, participant decision, lost to follow-up)	Treatment policy	Ignore the occurrence of intercurrent events (use observed outcome)		
	Use of rescue medication	Composite policy	Use of rescue medication means never achieve symptom alleviation (censor at Day 14)		
	Hospitalization for the treatment of COVID-19 or all-cause death	Treatment policy	Ignore the occurrence of intercurrent events (use observed outcome)		
Proportion of participants with negative SARS-CoV-2 nasal swab viral load at Days 3, 5, 10, 15 Proportion of participants with negative SARS-CoV-2 nasal swab infectious viral titer at Days 3, 5, 10, 15	Discontinue randomized treatment prior to endpoint (due to AE, lack of efficacy, investigator's discretion, noncompliance with study drug, protocol violation, participant decision, lost to follow-up)	Treatment policy	Ignore the occurrence of intercurrent events (use observed outcome)		
,	Use of rescue medication	Composite policy	Use of rescue medication means never achieve negativity		

AE = adverse event; COVID-19 = coronavirus disease 2019; MAVs = medically attended visits

6.5. Changes From Protocol-Specified Efficacy Analyses

An interim analysis of safety, futility and efficacy was planned in the protocol using the O'Brien-Fleming approach when 50% (1150 participants) of planned participants completed the Day 29 assessment or prematurely discontinued from the study. The second DMC meeting was to include review of the interim analysis results. Due to early stopping of enrollment of this study, the planned interim analysis was not conducted. The second and any following DMC meeting were not held.

The primary analysis set for efficacy analyses was specified as the FAS in the protocol, but will be the FAPS per FDA feedback.

The secondary endpoints of all-cause hospitalization by Day 29 and COVID-19–related MAVs by Day 29 were to be analyzed using a competing risk analysis approach, with death as the competing risk as described in the protocol. Competing risk analysis approach will not be used due to very low event rate for deaths.

Sensitivity analyses for the primary endpoint that were specified in the protocol will not be conducted.

The questionnaires to assess the impact on work productivity, activities of daily living, and functionality, WPAI + CIQ: COVID-19 and PROMIS-29, were not available to any participants by the time of stop of enrollment. Data for these questionnaires were not collected and statistical analysis will not be conducted.

7. SAFETY ANALYSES

7.1. Adverse Events and Deaths

7.1.1. Adverse Event Dictionary

Clinical and laboratory AEs will be coded using the current version of MedDRA. SOC, high-level group term (HLGT), high-level term (HLT), PT, and lowest-level term (LLT) will be provided in the AE dataset.

7.1.2. Adverse Event Severity

The severity of AEs will be graded using the Division of AIDS (DAIDS) Table for Grading the Severity of Adult and Pediatric Adverse Events, Version 2.1 dated July 2017. For each episode, the highest grade attained should be reported as defined in the grading scale. The DAIDS scale is available at the following location:

https://rsc.niaid.nih.gov/sites/default/files/daidsgradingcorrectedv21.pdf

Adverse events are graded by the investigator as Grade 1 (mild), Grade 2 (moderate), Grade 3 (severe), Grade 4 (life threatening) or Grade 5 (fatal) according to toxicity criteria specified in the document above. The severity grade of events for which the investigator did not record severity will be categorized as "missing" for tabular summaries and data listings. The missing category will be listed last in summary presentation.

7.1.3. Relationship of Adverse Events to Study Drug

Related AEs are those for which the investigator selected "Related" on the AE CRF to the question of "Related to Study Treatment." Relatedness will always default to the investigator's choice, not that of the medical monitor. Events for which the investigator did not record relationship to study drug will be considered related to study drug for summary purposes. However, by-participant data listings will show the relationship as missing.

7.1.4. Serious Adverse Events

Serious adverse events (SAEs) will be identified and captured as SAEs if the AEs met the definitions of SAEs that were specified in the study protocol. SAEs captured and stored in the clinical database will be reconciled with the SAE database from the Gilead Global Patient Safety Department before data finalization.

7.1.5. Treatment-Emergent Adverse Events

Incidence of treatment-emergent adverse events (TEAEs) and laboratory abnormalities, and incidence of SAEs, and AEs leading to study drug discontinuation are secondary safety endpoints of this study.

7.1.5.1. Definition of Treatment-Emergent Adverse Events

TEAEs are defined as 1 or both of the following:

- Any AEs with an onset date on or after the study drug start date and no later than 30 days after permanent discontinuation of study drug
- Any AEs leading to premature discontinuation of study drug.

7.1.5.2. Incomplete Dates

If the onset date of the AE is incomplete and the AE stop date is not prior to the first dosing date of study drug, then the month and year (or year alone if month is not recorded) of onset determine whether an AE is treatment emergent. The event is considered treatment emergent if both of the following 2 criteria are met:

- The AE onset is the same as or after the month and year (or year) of the first dosing date of study drug, and
- The AE onset date is the same as or before the month and year (or year) of the date corresponding to 30 days after the date of the last dose of study drug.

An AE with completely missing onset and stop dates, or with the onset date missing and a stop date later than the first dosing date of study drug, will be considered to be treatment emergent. In addition, an AE with the onset date missing and incomplete stop date with the same or later month and year (or year alone if month is not recorded) as the first dosing date of study drug will be considered treatment emergent.

7.1.6. Summaries of Adverse Events and Deaths

Treatment-emergent AEs will be summarized based on the Safety Analysis Set.

The number and percentage of participants who experienced at least 1 TEAE will be provided and summarized by SOC, HLT (if applicable), PT, and treatment group. For other AE categories described below, summaries will be provided by SOC, PT, and treatment group:

- Grade 3 or higher TEAEs
- All treatment-emergent treatment-related AEs
- Grade 3 or higher treatment-emergent treatment-related AEs
- All treatment-emergent SAEs
- All treatment-emergent treatment-related SAEs
- All treatment-emergent AEs leading to premature discontinuation from study drug

TEAE and treatment-related TEAE will be summarized by SOC, PT, severity, and treatment group.

A brief, high-level summary of the number and percentage of participants who experienced at least 1 TEAE in the categories described above will be provided by treatment group. All treatment-emergent deaths observed in the study will also be included in this summary. Treatment-emergent death refers to deaths that occurred between the first dose date and the last dose date plus 30 days (inclusive).Multiple events will be counted only once per participant in each summary. Adverse events will be summarized and listed first in alphabetic order of SOC (and HLT within each SOC if applicable), and then by PT in descending order of total frequency within each SOC. For summaries by severity grade, the most severe grade will be used for those AEs that occurred more than once in an individual participant during the study.

In addition to the above summary tables, all TEAEs, Grade 3 or higher TEAEs, treatment-emergent treatment-related AEs, Grade 3 or higher treatment-emergent treatment-related AEs, and treatment-emergent SAEs, will be summarized by PT only, in descending order of total frequency.

In addition, data listings will be provided for the following:

- All AEs, indicating whether the event is treatment emergent
- Treatment-related AEs
- All AEs with severity of Grade 3 or higher
- All SAEs
- All Deaths
- Treatment-related SAEs
- All AEs leading to premature discontinuation of study drug

